## JHM IRB - eForm A – Protocol

- Use the section headings to write the JHMIRB eForm A, inserting the appropriate material in each. If a section is not applicable, leave heading in and insert N/A.
- When submitting JHM IRB eForm A (new or revised), enter the date submitted to the field at the top of JHM IRB eForm A.

\*\*\*\*\*

### 1. Abstract

Postmenopausal women are disproportionately impacted by urinary tract infection (UTI), particularly chronic recurrent UTI (rUTI), defined as UTIs that recur  $\geq 2$  times per 6 months. Presently, the only evidence-based prevention options are daily low dose antibiotics and topical vaginal estrogen therapy (VET). Given concerns related to chronic antibiotic use, VET is preferred for postmenopausal women. Unfortunately, 50% of women experience recurrence despite VET. It is unknown why some women benefit from VET while others do not. Also, the mechanism by which VET, when effective, prevents rUTI is uncertain. This study seeks to identify mechanisms that explain how VET reduces rUTI among postmenopausal women for whom VET is a preferred therapy.

The purported mechanism is via changes to the vaginal microbiome, possibly related to restoration of Lactobacilli. This may be due to production of D-Lactic acid, which suppresses vaginal growth of uropathogens such as *E. coli*. (This increased production of lactic acid is reflected by vaginal pH, which is typically reduced with VET use.) It has also been suggested that the beneficial effects of VET are mediated by changes in the *urinary* microbiome. Finally, recent studies (mostly in mice) suggest that host immune responses in the bladder and urogenital tract are critical to rUTI susceptibility, symptoms, and outcomes.

To investigate the mechanisms by which VET reduces rUTI, we will conduct a single-arm, open-label clinical trial of conventional therapy with vaginal estrogen therapy for postmenopausal women with rUTI. These are women who would be recommended (as a part of routine clinical care) to receive VET for rUTI prevention. Among 50 women with confirmed rUTI, we will investigate (a) the effects of vaginal estrogen therapy on the bladder and vaginal microbiota (as well as D- and L-lactic acid concentrations in the vagina) and (b) the effects of vaginal estrogen therapy on immune responses in both compartments (including soluble mediators of inflammation (SMI) associated with neutrophil and macrophage activity and those associated with Th1, Th2 and Th17 pathways). Over 24 weeks, we will then identify the subset of participants who continue to experience rUTI versus those who respond to vaginal estrogen therapy. Comparing these two groups, we will consider (c) the extent to which changes in microbiota and immune responses are associated with successful UTI prevention.

### 2. Objectives (include all primary and secondary objectives)

The three aims of this proposal are:

1. **To compare the vaginal and urinary microbiota before and after VET in women with rUTI.** Hypothesis: After VET, vaginal and urinary microbiota will exhibit

*significantly increased relative abundance of key Lactobacillus spp. (L. crispatus, L. gasseri, L. jensenii, L. iners). Vaginal D-lactic acid concentration will increase and pH will decrease.*

**2. To compare host immune responses, by measuring vaginal and urinary soluble mediators of inflammation (SMIs), before and after VET in women with rUTI.**

*Hypothesis: after VET, vaginal and urinary samples will show decreased SMIs associated with neutrophil and macrophage activity and Th2-associated cytokines, with concomitant increases in Th1 and Th17 related pathways.*

**3. To acquire preliminary data regarding vaginal and urinary markers that distinguish women who remain UTI-free after VET versus those who continue to experience UTI recurrence**

**3. Background** (briefly describe pre-clinical and clinical data, current experience with procedures, drug or device, and any other relevant information to justify the research)

Each year in the U.S., urinary tract infection (UTI) is the cause of 8 million ambulatory and 1 million ED visits. Postmenopausal women are disproportionately impacted: 13% of female Medicare beneficiaries experience  $\geq 1$  UTI annually. Furthermore, among older women who experience UTI,  $>40\%$  experience chronic recurrent UTI (rUTI) (defined as UTIs that recur  $\geq 2$  times per 6 months or  $\geq 3$  per 12 months). Prevention of UTI recurrence is crucial for older women with rUTI, yet effective options are limited. **American Urologic Association guidelines recommend two options to reduce recurrence: vaginal estrogen therapy (VET) or daily low dose antibiotics. While daily antibiotic prophylaxis is effective, concerns regarding side effects and emergence of antibiotic resistance limit its use. Thus, VET prophylaxis is first line for rUTI prevention in postmenopausal women.** Several clinical trials demonstrate that 50% of women will continue to experience rUTI recurrence despite VET. At present, it is unknown why some women benefit while others do not and the mechanisms for treatment success are unknown.

**The first aim** of this protocol is to investigate the effect of VET on urogenital microbiota. The rationale is that changes to the vaginal microbiome are purportedly critical to rUTI susceptibility. The vagina is a reservoir for uropathogens (e.g. E. coli). Vaginal lactobacilli may protect against rUTI through a variety of mechanisms, including displacement of uropathogens by competitive binding and direct inhibition of bacterial growth, likely through the bactericidal action of lactic acid. There may be other important functional parameters of the microbiome that influence UTI risk (e.g., features that can be best understood through metabolomics, proteomics, etc.).

Measures for Aim 1 are as follows:

**Vaginal microbiota:** After menopause, vaginal colonization by lactobacilli declines. There is some evidence that VET restores vaginal Lactobacilli. Prospective studies linking a lactobacillus-dominant microbiome to UTI prevention are lacking. Also, new data from studies using contemporary molecular techniques (e.g., 16S rRNA gene amplicon sequencing, shot gun or whole genome metagenomics, RNA-seq) suggest that some Lactobacillus species (and certain vaginal “community state types”) may be more likely than others to reduce UTI recurrences.

**Vaginal D-Lactic acid and pH:** Differences in the vaginal microbiota may be linked to production of d-lactic acid. This isomer is produced more effectively by certain lactobacillus species (most notably *L. crispatus*). Therefore, for aim 1, we propose to

compare the vaginal microbiota and d-lactic acid concentrations before and after 12 weeks of VET among women with rUTI. Vaginal pH will also be examined, as this bedside test may prove to be a valuable (bedside) diagnostic test, reflecting d-Lactic acid and other markers. Vaginal pH >5 is typical for menopause and a restoration of acidic pH provides additional evidence of adequate estrogenization.

In addition, we hope to expand our analyses to complement these microbiota analyses with additional functional (e.g., metabolomic, proteomic) analyses.

**Vaginal estrogen status:** The vaginal maturation index (VMI) is a measure of vaginal “estrogenization”, which we will collect at enrollment and after 12 weeks of VET. This is based on a cytologic examination of vaginal epithelial cells, obtained via a swab of the vaginal wall. The VMI is a widely used objective and quantitative measure of vaginal estrogen status. Collection of this marker will allow us to establish how these conventional measures of estrogenization compare to other study outcomes, such as changes to urogenital microbiota and immune response.

**Urinary microbiota:** In addition, there is some evidence that the composition of urinary microbiota may influence rUTI. For example, a preoperative urinary microbiome deficient in lactobacilli and high in uropathogens has been associated with postoperative UTI. For aim 1 we also plan to compare the urinary microbiota before and after 12 weeks of VET among women with rUTI.

**The second aim** of this research is to investigate the effect of VET on the localized immune response in the vagina and bladder. Finally, there is evidence (primarily from animal models) that the host immune response is critical to rUTI susceptibility. For example, bladder invasion by uropathogens is 10–12 fold greater in Toll like receptor 4 mutant mice versus wild type. Also, in a murine model, severe acute immunopathology (with elevated IL-6 and IL-8 in response to UTI), predicts chronic cystitis and rUTI susceptibility. Also, importance of Th1 versus Th2 pathway activation is demonstrated by IFN- $\gamma$  knockout mice (unable to mount a Th1 response): these mice have an increased incidence and severity of UTI, are vulnerable to re-infection, and are less able to clear bacteria when re-challenged after initial infection. In contrast IL-4 knockout mice (Th2 impaired, Th1 uninhibited), appear to be protected from re-infection. Given the apparent importance of the host immune response to UTI susceptibility, it is relevant that some aspects of immune response may be modified by estrogen. For example, consider gender differences in UTI susceptibility: among mice infected via transurethral catheter, males develop higher bacterial burdens than females, possibly because males lack a robust increase in inflammatory cytokines (notably IL-17). Additional evidence of estrogen's protective effect comes from ovariectomized mice, which show increased bacteriuria, IBC's, and pro-inflammatory (Th2 associated) IL-6 compared with sham-operated females. Human data are limited, although it has been shown that serum IL-6 increases with menopause and decreases with systemic estrogen therapy. Also, in non-rUTI populations vaginal levels of the pro-inflammatory cytokine TNF- $\alpha$  decreases with VET.

**Therefore, for aim 2, we plan to compare vaginal and urinary fluid from before versus after 12 weeks of VET for soluble mediators of inflammation (SMIs),** including those associated with neutrophil and macrophage activity and those associated with Th1, Th2 and Th17 pathways.

[figure not shown]
Aims 1 and 2 will identify “biomarkers” that are significantly impacted by VET. **The goal of Aim 3 is to compare these biomarkers between women who continue to experience rUTI versus those who remain UTI-free on VET.** These comparisons will provide preliminary data to support a future RCT of VET in women with rUTI. Specifically, those bio-markers which show the greatest promise to distinguish successful rUTI

prevention will then be rigorously evaluated in a future larger and adequately powered clinical trial to definitively identify the predictors of and the biological conditions associated with successful prevention of UTI recurrence among susceptible women.

#### 4. Study Procedures

- a. Study design, including the sequence and timing of study procedures (distinguish research procedures from those that are part of routine care).

All three aims of this proposal will be accomplished via a **single-arm, open label clinical trial** of transvaginal estrogen to reduce UTI recurrence among menopausal women with confirmed rUTI (see figure below). Briefly, 24 weeks of vaginal estrogen treatment will be administered to 50 eligible postmenopausal women with a history of rUTI. Aims 1 and 2 will be accomplished after 12 weeks of VET (because 12 weeks may be required for adequate estrogenization. Aim 3 will be accomplished during the second 12-week interval of VET.

There is only one arm in this trial -- all participants will receive VET (which meets the standard of care for therapy in women with rUTI). A placebo arm is not considered because it would not be relevant to our scientific aims. A strength of the study design is that for Aim 1-2 and Aim 4 participants are compared to themselves, minimizing the effect of potential confounders. For Aim 3, the operative question is what distinguishes women who respond to VET vs. those who do not. These scientific reasons justify the single arm study design. This study meets the NIH definition for "Clinical Trials", defined as a clinical research study (a) in which human participants are assigned to an intervention, (b) the study evaluates the effect(s) of the intervention on the participants, and (c) the effect being evaluated is a health-related biomedical outcome.

The vaginal estrogen treatment (VET) to be administered in this study is a conventional treatment that is commercially available. In general, VET may be administered as a cream, vaginal tablet or silicone ring. This study will use vaginal estradiol tablets (10mcg), administered daily for two weeks, followed by twice weekly.

For those who enroll, study procedures will include the collection of urinary and vaginal specimens (see below) at enrollment (before VET initiation) and after 12 weeks of therapy. The primary difference between this study and our routine clinical care is specimen collection. We will also track rUTI episodes during the first 24 weeks of VET (but the evaluation and treatment of those episodes will follow best practices in clinical care and will not be impacted by participation in this study).

- b. If your study involves data/biospecimens from participants enrolled under other research studies with a written consent or under a waiver of consent, please list the IRB application numbers for those studies. Please note: Certificate of Confidentiality (CoC) protections applied to the data in source studies funded by NIH or CDC will extend to this new study if the funding was active in 2016. If this situation applies, Section 36, question 6 in the application will need to be answered “Yes” and “Hopkins Faculty” should be selected in question 7. No other documents are required.

Not applicable.

- c. Study duration and number of study visits required of research participants.

The study will last 24 weeks. Study procedures will be timed to coincide with routine clinical visits (baseline, 12 weeks, 24 weeks). Participation in this study will not require additional visits (outside of what is required for clinical care).

At baseline, women will be screened for eligibility at a routine clinical visit. Those found to be eligible will be consented and enrolled. Women who initiate VET for UTI prevention are typically seen for clinical care 3 and 6 months after VET initiation (e.g., 12 and 24 weeks). For this proposed research, we will collect study specimens at the visit prior to VET initiation and at the 12-week follow up visits. No specimens will be collected at the 24 week visit.

- d. Blinding, including justification for blinding or not blinding the trial, if applicable.

Not applicable. All participants and investigators will be aware of the study treatment (vaginal estradiol tablets).

- e. Justification of why participants will not receive routine care or will have current therapy stopped.

Participants will receive the same VET regimen that would be prescribed as part of clinical care, including standard dosing. VET complies with best practices for rUTI prevention, as recommended by the American Urologic Association.

- f. Justification for inclusion of a placebo or non-treatment group.

A placebo arm is not considered because it would not be relevant to our specific aims. The rationale is discussed above (see 4a).

- g. Definition of treatment failure or participant removal criteria.

When VET is recommended in clinical practice, a 6-month trial is typical (to assess response). This study is limited to that 6-month period. Of course, some women may elect to stop VET during the observation period, possibly due to intolerance or dissatisfaction with the treatment. (Similarly, women receiving VET in clinical practice may elect to stop this Rx.) Participation in this study will not impact a decision to stop VET before the 6-month period is completed. Women who elect to stop VET will be encouraged to continue in the trial (to allow data collection as proposed).

- h. Description of what happens to participants receiving therapy when study ends or if a participant's participation in the study ends prematurely.

At the conclusion of this trial, women will have the opportunity to continue VET as part of their clinical care. They will be informed that their prescription insurance coverage may or may not cover this treatment. Those who are not satisfied with VET will be offered alternative prevention options (such as daily antibiotic suppression).

- i. If biological materials are involved, please describe all the experimental procedures and analyses in which they will be used.

Study procedures will be the same for the enrollment and subsequent visits. All study specimens will be labeled with a sample ID barcode, the visit type (enrollment, 12-week) and the study ID assigned to the participant.

1. Vaginal pH: A mid-vaginal swab will be used to measure pH using Nitrazine pH test paper.
2. Vaginal Maturation Index (VMI): A spatula will be used to collect a specimen from the lateral vaginal wall. The tip of the spatula will be placed in a SurePath Pap Collection vial and transported to the Pathology department for processing
3. Specimens to be frozen\* and stored for later analysis:
  - i. Vaginal microbiota: a mid-vaginal swab will be obtained and placed in 1ml stabilizing buffer solution.
  - ii. Vaginal SMI and D/L lactic acid: a mid-vaginal swab will be obtained and stored dry.
  - iii. Urinary microbiota and SMI: A urine specimen will be obtained with a 14F catheter. 10cc will be obtained and aliquoted (4ml reserved for microbiota and 2ml for SMI analysis). Note: We do not expect a *clinical* indication for urinary catheterization at the 24 week visit. Therefore, a catheterized urine specimen will not be collected at 24 weeks unless clinically indicated.

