## 8. Risks

- a. Medical risks, listing all procedures, their major and minor risks and expected frequency.
- b. Steps taken to minimize the risks.
- c. Plan for reporting unanticipated problems or study deviations.
- d. Legal risks such as the risks that would be associated with breach of confidentiality.
- e. Financial risks to the participants.

Participation in this study is felt to represent minimal risk to participants. All women enrolled in this trial will be receiving a medication that is commonly prescribed in clinical practice. This medication (vaginal estrogen) is felt to be safe and effective in the treatment of postmenopausal vaginal atrophy and is currently recommended by the American Urologic Association as a best practice for preventing recurrent UTI.

The collection of specimens (vaginal swabs and urine specimens) represents minimal harm to participants. Such specimens are often collected for clinical care in the setting of the evaluation and management of recurrent UTI.

To protect participant privacy and confidentiality, data management will be via Red Cap and CRMS. All collected specimens will be labeled with the participant's study number. The log that links each participant to the assigned study number will be kept electronically in CRMS.

Review of the EMR will be required to gather data regarding patients' clinical course and observed UTI recurrences. Data from chart abstraction will be collected via RedCap. Only IRB-approved members of the study team will have access to these data. No identifiable information will be stored on private devices or directly on computers or other electronic devices. "Paper documents containing patient information (such as signed consent documents) will be uploaded electronically but the original hard copies will also be retained in accordance with institutional policy."

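### Specimen labels carry the visit type, and nothing masks the cytology reader or laboratories or keeps a woman's two specimens in the same run: a cheap improvement for an uncontrolled before-after comparison

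*Combined protocol and SAP*

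**What the plan says.** - **Label.** Section 4i has all study specimens "labeled with a sample ID barcode, the visit type (enrollment, 12-week) and the study ID assigned to the participant".
- **Timing.** Section 4c: "we will collect study specimens at the visit prior to VET initiation and at the 12-week follow up visits". Nothing is collected at 24 weeks, so the two visit types are exactly pre and post.
- **Design.** Section 4a describes a "single-arm, open label clinical trial", with each woman compared with herself for Aims 1 and 2.
- **Blinding.** Section 4d: "Not applicable. All participants and investigators will be aware of the study treatment (vaginal estradiol tablets)". It does not mention the people who read or assay specimens.
- **VMI.** Section 3 (Vaginal estrogen status): "This is based on a cytologic examination of vaginal epithelial cells". The same paragraph sets VMI up as the conventional measure against which changes in microbiota and immune response are viewed. Section 4i sends the vial to Pathology.
- **Assays.** Section 12b sends de-identified specimens to an external laboratory for microbiome and lactic acid work, and keeps them frozen until the target number is reached. Section 4 (Aim 2) plans a Luminex multiplex for the soluble mediators.
- **Analysis.** Section 7 tests the pre-to-post change in Lactobacillus abundance, D-lactic acid and each soluble mediator. It specifies no test of VMI.

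**The concern.** Comparing a woman with herself removes stable differences between women. It does not remove a measurement shift that follows the visit. With one arm, no untreated pair of specimens would reveal such a shift, so it would be counted as an effect of VET.

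There are two routes. A cytology reader who sees the visit knows which way the maturation index is expected to move. In the laboratories, the visit could line up with plate or run, or could colour decisions on repeats and exclusions. Section 3 carries the markers identified in Aims 1 and 2 into Aim 3 and towards a future randomised trial, so a spurious marker would travel with them.

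Open-label treatment explains why participants and clinicians know what is given. It gives no reason for Pathology or the laboratories to know the visit.

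**Working it through.** **Step 1. The plan's own figures.** Section 7 gives 95% half-widths of ±12.9% (n = 40) and ±11.6% (n = 50) for the mean change in vaginal Lactobacillus abundance, without the SD. Solving SD = half-width × √n / 1.96:

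- n = 40: 12.9 × 6.325 / 1.96 = 41.6 points
- n = 50: 11.6 × 7.071 / 1.96 = 41.8 points

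With SD 41.8, a two-sided paired t-test at 80% power detects 19.0 points at n = 40 and 16.9 at n = 50. This matches the stated 17% to 19%. The sample-size figures are therefore consistent for 40 to 50 women; the present point does not depend on them.

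**Step 2. What the text establishes.**

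| Question | Where | Answer |
|---|---|---|
| Is the visit on the label? | 4i | Yes, on all study specimens |
| Does the visit equal pre/post? | 4c | Yes, two collection times only |
| Is masking of readers or laboratories stated? | 4d, 4i, 12b | No |
| Is pairing of runs or random run order stated? | 4i, 7, 12b | No |
| Is plating by visit stated? | 4i, 7, 12b | No |
| Is there a control arm? | 4a | No |

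**Step 3. Illustration of a reading shift.** From the documents: 40 to 45 complete pairs and alpha 0.05, taken as two-sided. Assumed: a systematic shift of b SDs of the paired change, and no true change. The rejection rate is that of a paired t-test with noncentrality b√n, counting both tails.

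| b (assumed) | b√n at n = 40, 45 | Rejection rate at n = 40, 45 |
|---|---|---|
| 0.1 | 0.63, 0.67 | 9.5%, 10.1% |
| 0.2 | 1.26, 1.34 | 23.5%, 25.9% |
| 0.3 | 1.90, 2.01 | 45.7%, 50.3% |

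**Step 4. Illustration of a batch shift, if plates were split by visit.** Everything here is assumed: SD of the ln change 1.0, 42 pairs (within the planned 40 to 45), between-plate SD s of 0.1 to 0.3 ln units, and k = 1 or 2 plates per visit. Then se² = 1/42 = 0.0238, τ² = 2s²/k, and the rejection rate is 2 × [1 − Φ(1.96 × se / √(se² + τ²))].

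- s = 0.1, k = 2: τ² = 0.01; ratio se / √(se² + τ²) = 0.839; rate 10%
- s = 0.3, k = 1: τ² = 0.18; ratio 0.342; rate 50%

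Running both specimens of a pair on one plate removes this term, because the plate effect cancels in the difference. Taking the visit off the label does not remove it by itself.

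**The case against.** The strongest reply has five parts.

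1. *The label is not proof of what analysts see.* A barcode exists, specimens going to the external laboratory are de-identified, and that laboratory receives no data from the site. This stands in part. That a reader knows the visit is an inference; the documents show only that the label states it and that no masking is described. De-identification concerns the woman's identity and does not say that the visit is removed.
2. *The primary outcome is instrument-based.* This stands. On the SD of about 41.8 points, a shift of 0.1 to 0.3 SD would be about 4 to 13 points of relative abundance, and no mechanism is shown by which a tube label would produce that through reading. For sequencing, lactic acid and Luminex, the route is batching, repeats and exclusions.
3. *VMI has no test in Section 7.* This also stands. The rates in Step 3 belong to no planned VMI test. What is at risk is VMI's role as the estrogenization comparator.
4. *The visit on the tube guards against pre/post swaps.* This is fair, and any change must replace that safeguard.
5. *Masking would be incomplete.* Vaginal pH is read from test paper, which Section 3 calls a bedside test, so relabelling does not mask it. If VMI vials are read on arrival, reading order may still hint at the visit.

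Two stronger readings should be resisted. A reader might infer that Section 8 contradicts Section 4i, since it says "All collected specimens will be labeled with the participant's study number". But it does not say that nothing else is on the label, and the Section 4i label also carries the study ID, so both statements can be true. A reader might also infer that specimens will be plated by visit. No section says so, and frozen storage until recruitment is complete makes paired runs feasible.

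**Conclusion.** The point holds as a cheap improvement to a stated rule, not as evidence of bias. Section 4i puts pre/post status on every specimen, and no section masks the cytology reader or the laboratories or keeps pairs together. Without a control arm, a visit-linked shift could not be separated from a VET effect. Exposure to a reading shift is mainly in VMI; exposure to a batch shift is in sequencing, lactic acid and Luminex.

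The size is unknown. The range of about 9.5% to 50% against a nominal 5% rests on assumed shifts of 0.1 to 0.3 SD, and the 10% to 50% for plates split by visit rests on assumed plate effects and a layout the plan does not describe. Only the number of pairs and alpha come from the documents. The figures show that modest shifts matter at 40 to 45 pairs; they do not show that such shifts will occur.

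**What to change.** Amend Section 4i as follows:

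- Send specimens to Pathology and the laboratories under a non-sequential barcode without visit type. The study team holds the barcode-to-visit key until laboratory data are final.
- Score the VMI without knowledge of the visit.
- Run each woman's two frozen specimens on the same plate or sequencing run, in random order.

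This adds no visit, assay or participant and leaves the sample size unchanged. It does require a revised label, a few sentences, a run-order list and a key-release step. The visit must be looked up from the barcode when a specimen is queried. A check against swaps is also needed, for example reconciling barcodes to visits at collection and again before shipment, because the tube no longer shows the visit. The plan should acknowledge that bedside pH remains unmasked and that VMI reading order may give a hint if vials are read as they arrive. The change has to be made before specimens are read or assayed, since masking cannot be restored afterwards.
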